3.4. Patient Selection**3.4.1. Inclusion Criteria**

Inclusion Criteria are described in Section 5.1 of the clinical study protocol.

3.4.2. Exclusion Criteria

Exclusion Criteria are described in Section 5.2 of the clinical study protocol.

3.5. Determination of Sample Size

This is an open-label study to determine safety and tolerability of AP01 50 mg once daily or 100 mg twice daily; both regimens being administered using the eFlow. With 50 patients per group, we have a 92% chance of detecting an AE with a true population rate of 5%, as displayed in Table 1:

Table 1: Probability of observing adverse events

	Actual probability of event		
	1%	5%	10%
Chance of observing ≥ 1 event	0.395	0.923	0.995

The Phase 3 study of oral pirfenidone in patients with IPF (ASCEND)¹ showed a standard deviation (SD) of 4.5 based on the imputed mean change in % of predicted FVC at Week 26. Assuming a SD of 4.5, with 50 patients per group, a two-sided 95% confidence interval (CI) for mean change from baseline in % of predicted FVC will extend 1.25 from the observed mean. The ASCEND¹ study showed a decrease of 1.5 and 3.9 in % of predicted FVC at Week 26 in the pirfenidone and placebo groups, respectively. Table

This document is confidential.

SAP Version: 3.0 (15JUL2021)
Controlled Document ID: **3903A.01**, Effective Date 29-Oct-2018
Filing requirements: TMF

Page 14 of 52

Statistical Analysis Plan

Sponsor: Avalyn Pharma, Inc.; Protocol No.: AP01-002

2 shows results of the ASCEND¹ active and placebo groups and potential observed differences in the AP01-002 study, assuming a similar SD.

Because we have no prior data on efficacy outcomes with our compound, we are unable to make well-informed predictions of effect size or variability. In lieu of that information, we have included some estimates of confidence intervals based on prior oral pirfenidone studies; however, we cannot be confident that our product will behave similarly and would not base hypothesis tests on this information. This study will give us an idea of which endpoints are most likely to be positively impacted by our product as well as solid estimates of both effect size and variability. In addition, if the effect is due to AUC or multiple peaks/day in the Epithelial Lining Fluid (ELF) rather than peak levels, based on our modeling from the BAL cohort in the AP01-001 study, we have around 75% power to show a difference between groups. With this sample size, we can be confident on selecting dosing regimen(s) for future trials.

Table 2: Observed and potential change in FVC

	ASCEND¹ Placebo (n = 262)	ASCEND¹ Active (n = 255)	AP01-002 Potential Scenarios (n = 50)		
Observed Change FVC % predicted (mean, SD)	-3.9, 5.2	-1.5, 4.5	-0.75, 4.5	-1.0, 4.5	-1.5, 4.5
95% CI	(-4.53, -3.27)	(-2.05, -0.95)	(-2.0, 0.5)	(-2.25, 0.25)	(-2.75, -0.25)

3.6. Treatment Assignment & Blinding

Patients will be randomized in a 1:1 ratio to receive Pirfenidone Solution for Inhalation (AP01) either 50 mg once daily or 100 mg twice daily; both regimens being administered by the eFlow. The randomization schema will be stratified by region (Asia-Pacific and Europe) and by disease severity (FVC < 50% predicted and FVC ≥ 50% predicted). The first 20 patients randomized in the study must have FVC ≥ 50% predicted at Screening. After the first 20 patients have been randomized, patients with FVC 40% < 50% predicted will be allowed to be randomized in the study but randomization for these patients will be capped at 20.

This is an open-label study; no blinding restrictions are required.

3.7. Administration of Study Medication

Patients will be trained on use of the eFlow and administration of the study drug at the Baseline visit. The first dose of study drug for each patient will be administered and observed at the clinical study site at the Baseline visit to confirm tolerability. All subsequent doses will be administered by the patient at home. All doses must be taken at least 4 hours apart.

Patients who experience cough that limits their ability to complete dosing will be given 1 – 2 puffs (90 -

This document is confidential.

SAP Version: 3.0 (15JUL2021)
Controlled Document ID: **3903A.01**, Effective Date 29-Oct-2018
Filing requirements: TMF

Page 15 of 52

Statistical Analysis Plan

Sponsor: Avalyn Pharma, Inc.; Protocol No.: AP01-002

100 µg) of an inhaled beta 2 agonist, such as salbutamol, in order to complete the in-clinic dose. These patients, as well as patients with a history of asthma or smoking history of 20 pack years or greater, or patients that have a $\geq 15\%$ drop in FEV₁ % predicted in their pre-dose and post-dose readings and are symptomatic will be provided with and required to use 1 - 2 puffs (90 - 100 µg) of salbutamol prior to their second dose and for dosing throughout the study, unless these patients are currently taking a long-acting beta-2-agonist therapy. If symptoms persist with study treatment despite beta-2-agonist therapy, the Investigator will assess and discontinue the patient due to tolerability issues if he/she deems it necessary.

3.8. Study Procedures and Flowchart**3.8.1. Study Schedule**

The study schedule can be found in Tables 3 and 4. At-home patient assessments are outlined in Table 5. Detailed information on study assessments is provided in Section 7 of the clinical study protocol.

Table 3: Study Schedule for Part A

	Study Phase – Part A							
	Screening	Baseline	Treatment					
	1	2	3	4	5	6	7	8
Visit	1	2	3	4	5	6	7	8
Day	-30 to -1	1	28	56	84	112	140	168
Window (Days)	NA	NA	+/- 3	+/- 3	+/- 3	+/- 3	+/- 3	+/- 3
Informed Consent	X							
Eligibility Assessments	X	X						
Assessment of IPF Diagnosis	X							
Demographics	X							
Medical History	X							
Physical Exam ²	X	X	X	X	X	X	X	X
Height ³ , Weight	X				X			X
Vital Signs	X	X	X	X	X	X	X	X
ECG	X							
Laboratory Tests ⁴	X	X	X	X	X	X	X	X
Urinalysis	X	X	X	X	X	X	X	X
Urinary Pregnancy Test ⁵	X	X	X	X	X	X	X	X
Spirometry and D _{LCO}	X	X	X	X	X	X	X	X
SaO ₂	X		X	X	X	X	X	X
LCM ⁶ and diary dispensation	X				X			X
Cough VAS, KBILD Questionnaire and LCQ		X	X	X	X	X	X	X

This document is confidential.

SAP Version: 3.0 (15JUL2021)
 Controlled Document ID: **3903A.01**, Effective Date 29-Oct-2018
 Filing requirements: TMF

Page 16 of 52

Statistical Analysis Plan

Sponsor: Avalyn Pharma, Inc.; Protocol No.: AP01-002

HRCT ⁷		X						X
Pre-dose Spirometry		X						
Pre-dose SaO ₂		X						
Randomization		X						
Study Material Training		X						
Study Drug Administration First Dose		X						
Post-dose Spirometry (≤ 10 min post-dose)		X						
Post-dose SaO ₂		X						
Study Material Dispensation		X	X	X	X	X	X	X ⁸
Home Spirometer Training and Dispensation		X						
Concomitant Medications	X	X	X	X	X	X	X	X
Adverse Events		X	X	X	X	X	X	X
End of Treatment/Study Form								X

Table 4: Study Schedule for Part B

Visit	Study Phase – Part B				Follow-up
	Treatment				
	9	10	11	12	
Day	252	336	420	504 End of Study	28 days after End of Study
Window (Days)	+/- 7	+/- 7	+/- 7	+/- 7	+/- 7
Cough VAS, KBILD and LCQ	X	X	X	X	X
Physical Exam ²	X	X	X	X	X
Weight		X		X	
Vital Signs	X	X	X	X	X
Laboratory Tests ⁴	X	X	X	X	X
Urinalysis	X	X	X	X	X
Urinary Pregnancy Test ⁵	X	X	X	X	
Spirometry and DLCO	X	X	X	X	X

This document is confidential.

SAP Version: 3.0 (15JUL2021)
 Controlled Document ID: **3903A.01**, Effective Date 29-Oct-2018
 Filing requirements: TMF

Page 17 of 52

Statistical Analysis Plan

Sponsor: Avalyn Pharma, Inc.; Protocol No.: AP01-002

Saturated Oxygen	X	X	X	X	X
Study Material Dispensation	X	X	X		
Concomitant Medications	X	X	X	X	X
Adverse Events	X	X	X	X	X
End of Treatment/Study Form				X	X

Notes for Tables 3 and 4:

1. Follow-up visit will occur 28 days after the End of Study visit in Part B of the study.
2. A complete physical exam will be performed at Screening and Baseline visits. A modified physical exam including the patient's lungs and cardiovascular body systems will be performed at all other visits.
3. Height is collected at the Screening visit only.
4. Blood samples for laboratory tests include: Chemistry (including AST and ALT), Hematology and Biomarkers (Blood samples for biomarkers will not be collected at Screening.)
5. Females of childbearing potential are required to take a urinary pregnancy test at each visit except the Follow-up visit.
6. Patients that pass screening and are scheduled to be randomized will receive a LCM to be worn for 24 hours and returned to the site at the Baseline visit. LCM will be worn for 24 hours at Visits 5 and 8. A paper diary will also be dispensed to the patient to record activities during the 24-hour period.
7. HRCT scans will be performed at Visits 2 and 8. The Baseline HRCT may be skipped if the HRCT for eligibility was performed less than 1 month prior to the Baseline visit.
8. Study material dispensation will occur at Visit 8 for those patients participating in Part B of the study.

Table 5 Patient At-Home Assessments

DAILY: Patients will administer AP01 50 once daily or 100 mg twice daily
WEEKLY: Patients will perform home spirometry readings on the same day each week at approximately the same time of day (+/- 2 hours)

3.8.2. Study Visits

Part A will consist of one Screening visit and 7 study visits, within the 24-week treatment period. Part B will consist of quarterly visits through study termination. A Follow-up visit will occur 28 days after the patient's End of Study visit in Part B.

Details of Study Visits are described in Sections 6.2.1 through 6.2.10 of the clinical study protocol.

This document is confidential.

SAP Version: 3.0 (15JUL2021)
 Controlled Document ID: **3903A.01**, Effective Date 29-Oct-2018
 Filing requirements: TMF

Page 18 of 52

Avalyn Pharma, Inc.
AP01-002

Protocol v1.2
07 DEC 2018

4. Endpoints

4.1. Primary Efficacy Endpoint

- Change from baseline in absolute FVC % predicted.

4.2. Secondary Efficacy Endpoints

- Change from baseline in cough frequency as measured by LCM
- Change from baseline in the total KBILD score and in KBILD breathlessness and activity domains
- Change from baseline in the total LCQ score.
- Change from baseline in cough severity as measured by VAS
- Change from baseline in extent of fibrosis and lung volumes as assessed by HRCT
- Change from baseline in D_{LCO} .

4.3. Exploratory Endpoints

- Correlation between weekly home spirometry measurements and in-clinic spirometry values
- Correlation of extent of fibrosis and lung volumes as measured by HRCT at Baseline and Week 24 to other measures of clinical status, e.g. spirometry.
- Change from baseline in serum biomarkers of alveolar epithelial injury (CA19-9 and CA-125).

4.4. Safety Endpoints

- Treatment-emergent adverse events (AEs)
- Change from pre-dose to post-dose FEV₁ after initial dose
- Treatment-emergent deaths
- Treatment-emergent changes in clinical laboratory findings
- Changes in Vital signs.

Statistical Analysis PlanSponsor: Avalyn Pharma, Inc.; Protocol No.: AP01-002

5. Analysis Sets**5.1. Safety Set**

The Safety Set (SAF) will include all randomized patients who were administered at least one dose of study medication. Patients will be analyzed according to treatment received. The SAF will be used for all analyses of safety endpoints.

5.2. Full Analysis Set

The Full Analysis Set (FAS) will include all randomized patients. Patients will be analyzed according to randomized treatment. The FAS will be used for all analyses of patient disposition and baseline analyses and as a supportive sensitivity analyses for all efficacy endpoints. The FAS will also be used for the presentation of patients in all patient listings.

5.3. Per Protocol Set

The Per-Protocol Set (PP) will include all patients who were administered at least one dose of study medication, who have sufficient data to assess the primary efficacy endpoint, and who have no Major Protocol deviations that would impact the ability to appropriately assess the primary endpoint. Patients will be analyzed according to randomized treatment. Criteria for exclusion from the PP includes the following Major Protocol deviations:

- Violation of Inclusion/Exclusion Criteria
- Informed Consent not provided
- Study Drug Deviation
- Concomitant Medicine Restrictions

Summaries of all efficacy endpoints will be created using the PP.

5.4. Protocol Deviations

Protocol deviations will be collected and will be categorized as:

- Informed Consent
- Enrollment Criteria
- Dosing
- Concomitant Medications
- Visits/Procedures Required
- Visit Schedule
- Non-compliance
- Regulatory
- Laboratory
- Other

They will also be graded as Major or Minor.

This document is confidential.

SAP Version: 3.0 (15JUL2021)
Controlled Document ID: **3903A.01**, Effective Date 29-Oct-2018
Filing requirements: TMF

Page 20 of 52

Statistical Analysis PlanSponsor: Avalyn Pharma, Inc.; Protocol No.: AP01-002

Major protocol deviations are defined as a subset of protocol deviations that may significantly impact the completeness, accuracy, and/or reliability of the study data or that may significantly affect the subject's rights, safety or well-being. Major protocol deviations will be included in the Clinical Study Report (CSR). These include: Enrollment Criteria (violation of inclusion/exclusion criteria, Informed Consent (informed consent not provided), Dosing (study drug deviation), Non-compliance, Concomitant Medications (administration of prohibit medication) and Other Good Clinical Practice (GCP) deviations. All protocol deviations will be tracked and corrective live actions implemented.

Protocol deviations will be summarized by grade and category for each treatment group and overall in the following ways:

- Patients with Any Protocol Deviations (Major or Minor)
- Patients with Major Deviations Only
- Patients with Minor Deviations Only (i.e. excluding those patients with Major deviations).
- Protocol Deviations Attributable to COVID-19

All protocol deviations will be listed.

This document is confidential.

SAP Version: 3.0 (15JUL2021)
Controlled Document ID: **3903A.01**, Effective Date 29-Oct-2018
Filing requirements: TMF

Page 21 of 52

Statistical Analysis PlanSponsor: Avalyn Pharma, Inc.; Protocol No.: AP01-002

6. General Aspects for Statistical Analysis**6.1. General Methods**

Unless otherwise specified, all data will be summarized by treatment group and overall. A separate summary of data from Part A of will be provided in addition to a full study summary including both Part A and Part B data. Categorical data will be summarized as number and percent of total. Continuous data will be summarized using mean, median, SD and range. Dose response will be evaluated by comparing safety and changes in efficacy variables across the dose regimens.

All relevant patient data will be included in listings. All patients entered into the database will be included in patient data listings.

Pulmonary function tests (PFTs) (including D_{LCO}) are performed at each study visit.

The following PFTs will be performed at all visits (including Screening) using spirometry (and documented on the PFT eCRF form):

- FVC Liters (L)
- FEV₁ Liters (L)
- % Predicated FVC
- % Predicted FEV₁.

Pre-dose and post-dose spirometry will be performed at the Baseline visit.

At every visit, D_{LCO} ($\text{mL}/\text{min}^{-1}/\text{mmHg}^{-1}$) and % Predicted D_{LCO} will be obtained using the site's standard methodology.

FEV₁/FVC ratio will be derived as: $100 \times \text{FEV}_1/\text{FVC}$.

For comparisons to baseline, data from Visit 2 prior to the first dose of study drug will be used as baseline, unless otherwise noted. For PFTs, the pre-dose result will be used as baseline. Subgroup analyses will be performed based on baseline groupings for FVC, region, age, sex, D_{LCO} and progression-related biomarkers (CXCL13, CCL18, MMP3).

If either regimen is eliminated based on Part A outcomes, patients may be switched to the selected regimen for the remainder of their participation. Data summaries will be created to mimic this switch by using the following treatment grouping for Part B: (1) randomized to 100 mg twice daily; (2) randomized to 50 mg once daily and stayed on 50 mg once daily; (3) randomized to 50 mg once daily and switched to 100 mg twice daily; (4) randomized to 50 mg once daily total [groups 2 and 3 combined]; (5) overall total for Part B data. Descriptive within-patient analyses will be included for those patients who switch from 50 mg once daily to 100 mg twice daily. These analyses will include spider plots of change from baseline showing when the dose switch took place. Data listings will include a variable to denote the regimen switch and flag the time of the switch for affected patients.

No formal hypothesis tests are planned.

This document is confidential.

SAP Version: 3.0 (15JUL2021)
Controlled Document ID: **3903A.01**, Effective Date 29-Oct-2018
Filing requirements: TMF

Page 22 of 52

Statistical Analysis PlanSponsor: Avalyn Pharma, Inc.; Protocol No.: AP01-002

6.2. Key Definitions**6.2.1. First Dose Date**

First dose date in the study is defined as the first dose date of AP01 in Part A.

6.2.2. Cut-Off Date of Final Analysis

For the purpose of final analysis, the cut-off date of final analysis defined as the date at which all patients in the SAF either discontinue from treatment or 18 months has elapsed from the date of the first day of treatment for the last patient enrolled, whichever occurs first.

6.2.3. Baseline and Change from Baseline

Baseline is defined as the last non-missing measurement prior to or on the first dose of study drug.

Change from baseline = (post-baseline value – baseline value). For the purpose of tabulations, the unscheduled post-baseline values generally will be excluded.

6.2.4. Last Dose Date

The last dose date is defined as the last dose date of AP01 in Part B (or Part A if the patient discontinues treatment prior to Part B).

6.2.5. Study Day

The study day in the study is the days relative to the first dose date in the study. The day of the first dose of study medication in Part A will be defined as study day 1. The day prior to the first dose of study medication is study day -1. There is no study day 0.

6.2.6. First Dose Date of Part B

The first dose date of Part B is defined as first dose of study medication received after the Part A last dose date.

6.2.7. Treatment Duration

The overall treatment duration is defined as the last dose date – first dose date+1.

6.2.8. Dosing Switch Date

The dosing switch date is defined as the start date of the dosing change for those who switch from 50 mg once daily to 100 mg twice daily.

6.3. Missing Data

Missing values will not be imputed for data displayed in summary tables. For imputation of missing data used for the sensitivity analysis of the primary efficacy variable see Section 8.1.

Completely missing or partial dates will be presented in the listings as reported on CRFs.

If an AE has a completely missing onset date, then the AE will be considered a treatment emergent adverse event (TEAE). A medication with a completely missing start date is considered a prior medication. A medication with a completely missing stop date is considered a concomitant medication.

This document is confidential.

SAP Version: 3.0 (15JUL2021)
Controlled Document ID: **3903A.01**, Effective Date 29-Oct-2018
Filing requirements: TMF

Page 23 of 52

Statistical Analysis Plan

Sponsor: Avalyn Pharma, Inc.; Protocol No.: AP01-002

If an adverse event or a medication has a partial missing start or stop date, the following rules will be used to impute the date; then the imputed date will be used to determine whether it is a TEAE for adverse event, or a prior or concomitant medication.

Table 6: Partial Date Derivation

Partial Missing Start or Stop Date	Derived Start Date	Derived Stop Date
Missing month and day, and the year is present	January 1 of that year or first dose date if the year is the same as the year of first dose date	December 31 of that year
Missing day, but year and month are present	First day of that month or first dose date if the year and month are the same as the year and month of first dose date	Last day of that month
Missing month, but year and day are present	Missing month derived as January or same as first dose month if the year is the same as the year of first dose	Missing month derived as December

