7.6. Prior and Concomitant Medications and Therapies

Medications and therapies that started and stopped prior to the first dose of AP01 are considered as prior medications. Medications and therapies that started prior to the first dose of AP01 and continued into the treatment period are considered as prior and concomitant medications. Medications or therapies with a start date from first dose of AP01 to 30 days after administration of the last dose of AP01 will be considered as concomitant medications.

Prior and concomitant medications will be coded according to World Health Organization (WHO) Drug Dictionary (March 2018 WHO DDE (Enhanced) B2 Format) for Concomitant Medication. The concomitant medications will be summarized for each treatment group and overall by Anatomical Therapeutic Chemical (ATC) level 2 (Therapeutic Main Group) and ATC level 4 (Chemical/Therapeutic Subgroup) using the number and percentage of patients. Medications will be sorted in descending order of frequency of ATC level 2 and ATC level 4 within ATC level 2 in the overall total column. A patient will be counted only once within each level of summation if the patient has taken a medication more than once.

All prior and concomitant medications and therapies will be listed.

This document is confidential.

SAP Version: 3.0 (15JUL2021)
Controlled Document ID: **3903A.01**, Effective Date 29-Oct-2018
Filing requirements: TMF

Page 29 of 52

Statistical Analysis PlanSponsor: Avalyn Pharma, Inc.; Protocol No.: AP01-002

8. Efficacy

The following efficacy analyses will be performed:

- Change from baseline in absolute FVC % predicted
- Change from baseline in cough frequency as measured by LCM
- Change from baseline in the total KBILD score and in KBILD breathlessness and activity domains
- Change from baseline in the total LCQ score.
- Change from baseline in cough severity as measured by VAS
- Change from baseline in extent of fibrosis and lung volumes as assessed by HRCT
- Change from baseline in D_{LCO}

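### SAP Table 6 imputes partial start dates without checking the stop date or, when only the month is missing, the first-dose day, so some TEAE and prior/concomitant classifications come out wrong

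*SAP*

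**What the plan says.** SAP 6.3 says that when an AE or medication has a partial date the date is imputed, and "then the imputed date will be used to determine whether it is a TEAE for adverse event, or a prior or concomitant medication". Table 6 has three start-date rows:

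- Month and day missing: "January 1 of that year or first dose date if the year is the same as the year of first dose date".
- Day missing: "First day of that month or first dose date if the year and month are the same" as those of first dose.
- Month missing, day known: "Missing month derived as January or same as first dose month if the year is the same as the year of first dose".

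No start-date row mentions the stop date, and the third does not compare the recorded day with the day of first dose. For dates that are wholly missing, the same section treats an AE without an onset date as treatment-emergent, while for drugs "A medication with a completely missing start date is considered a prior medication".

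The classifications that use these dates are in SAP 7.6 and 10.1. In 7.6, "Medications and therapies that started and stopped prior to the first dose of AP01 are considered as prior medications", and a drug whose start falls on or after first dose (up to 30 days after the last dose) is concomitant. In 10.1, an AE is treatment-emergent if recorded during or after the start of AP01 administration.

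**The concern.** A rule that fixes the start without looking at the stop can contradict data already in the record. It can date the start of a drug or event after its recorded end, and the impossible start then decides the classification. The missing-month row can err the other way and drop an AE that may well have begun on treatment.

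The data needed for these errors are collected. AEs are recorded from informed consent (Protocol 7.4.1), screening may begin 30 days before Day 1, and drugs taken in the past 3 months are recorded at screening (Protocol 6.2.1). Events and drugs that ended before dosing will therefore be in the database.

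Safety is the primary objective, and TEAEs are the first safety endpoint listed. The tables at stake are the TEAE summaries and the concomitant-medication summary. In the latter, a drug stopped before dosing could appear as if taken during Part A.

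**Working it through.** The plan gives no figure to reproduce. The check applies Table 6 literally, with an assumed first dose of 20 June 2019 and on-treatment meaning a derived start on or after first dose.

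| Record | Known stop | Derived start | Class under Table 6 | What the record supports |
|---|---|---|---|---|
| Drug, start 2019 | 15 Mar 2019 | 20 Jun 2019 | Concomitant | Prior: ended about 3 months before dosing |
| AE, start Jun 2019 | 12 Jun 2019 | 20 Jun 2019 | TEAE | Not a TEAE: resolved before dosing |
| AE, day 10, month missing, 2019 | none | 10 Jun 2019 | Not a TEAE | Possibly post-dose |
| AE, day 25, month missing, 2019 | 1 Jun 2019 | 25 Jun 2019 | TEAE | Not a TEAE: latest possible onset is 25 May |
| AE, day 31, month missing, 2019 | none | 31 Jun 2019 | Undefined | Date does not exist |

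The first record is one the trial would collect: with screening on or before 15 June, a stop on 15 March falls within the 3-month look-back.

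**Rows 1 and 2.** When the match condition is met and the known stop precedes first dose, derived start = first dose > stop. This holds for every such record, by construction.

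**Row 3, third record.** Consent is at the earliest 30 days before dosing, 21 May. The possible dates to year end are the 10th of June to December, 7 in all, of which 6 are after 20 June. Table 6 picks the only pre-dose one. With no onset date at all, the same AE would be a TEAE.

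**How row 3 depends on the first-dose day.** Assume onsets uniform from first dose to 31 December, with only the month missing. For first dose on day d of June there are (31 − d) + 184 possible onset dates. Those on days 1 to d − 1 of July to December, 6 × (d − 1) of them, are moved before first dose:

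- d = 1: 0/214 = 0%
- d = 10: 54/205 = 26.3%
- d = 20: 114/195 = 58.5%
- d = 28: 162/187 = 86.6%

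Over every first-dose date in a 365-day year, 29,277 of 66,795 truly post-dose same-year onsets (43.8%) become non-TEAEs and 1,088 (1.6%) become invalid dates. These shares describe the rule under an assumed onset distribution and do not estimate anything in the trial.

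**The case against.** Moving an uncertain start to the first dose date is an accepted conservative convention when the stop date is unknown or post-dose. That stands: the fault in rows 1 and 2 is only the absent stop-date check. The affected tables are descriptive, SAP 6.3 lists partial dates as they were reported, and the Protocol asks for onset and resolution dates for AEs (10.1.4.3.1). A partial onset paired with a full pre-dose resolution date is a narrow case, and a known day with an unknown month is probably rarer still. All of this limits the size of the problem. Listing the raw date does not correct the class assigned in the tables. The before/after-dose flag in Protocol 10.1.4.3.1 is recorded for AEs on the date of first dose, and Table 6 does not use it.

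Four stronger readings are tempting, and the documents do not support them:

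- **That every partial start with a pre-dose stop is misclassified.** With the same first dose, a start of Feb 2019 and a stop of 15 Mar 2019 gives 1 Feb, correctly prior. Day 10 with the month missing and that same stop gives 10 Jun, also correctly prior.
- **That a stopped antifibrotic would remove a patient from the per-protocol set.** SAP 5.3 does list "Concomitant Medicine Restrictions" among the excluding deviations, but SAP 5.4 describes deviations as collected, categorised and graded. Nothing derives them from imputed dates. Protocol 5.3 bars these drugs within 3 days before randomization and during Part A, so a recorded stop in March is visibly compliant.
- **That about 48% of missing-month AEs are misclassified.** With both days uniform on 1 to 30, the chance that the recorded day precedes the first-dose day is 29/60 = 48.3%. That is the share dated before dosing, including AEs that truly were.
- **That year-only antifibrotic histories are common here.** No document says so. Intolerance is only one of several entry routes in Protocol 5.1.

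**Conclusion.** The point holds as a defect in a stated rule, and no other section overrides it. In rows 1 and 2, where the year or year and month match first dose, a known pre-dose stop always yields a start after the stop and a class that SAP 7.6 or the TEAE definition contradicts. In row 3, within the first-dose year, the error can go either way: an early recorded day can hide a post-dose AE, a later one can turn a resolved pre-dose event into a TEAE, and some derived dates are invalid. The loss of possible TEAEs is the less welcome direction for a safety study, and it sits oddly beside the rule for wholly missing onsets.

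The size in records is not stated and is probably small. That judgement rests on how seldom partial dates of these kinds are likely to occur, not on any count in the documents. The effect is on the TEAE and prior/concomitant tables. This is a minor correction, worth making because it is almost free.

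**What to change.** Amend SAP Table 6:

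- (a) In every row, if the known stop date is before first dose, classify the record as pre-dose (AE) or prior (drug). Never impute a start later than the known stop.
- (b) Otherwise keep rows 1 and 2 as they are, including the move to first dose on a match.
- (c) In the missing-month row, only when the recorded year is the first-dose year, use the later of the derived date and the first dose date, unless the stop is before first dose. If the derived date does not exist, first replace it with the last day of the first-dose month. Keep the January rule for other years.

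The limit to the first-dose year matters. Without it, a drug recorded as day 10, month missing, 2018 would move from 10 January 2018 to 20 June 2019, against its own recorded year.

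Applied to the five records above, the amended rule gives prior, not a TEAE, TEAE (20 June), not a TEAE, and TEAE (30 June). The cost is a few clauses in the SAP and a small programming change, with no new data collection.
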